## CURRENT AMENDMENT

Amendment Number	Amendment # 2 under CTIS	
Approximate Enrolled	115/300 patients (global)	
Reasons for Amendment	Primary reasons for Amendment:  Harmonization and correction of the statistical section, which referred to a 48-month inclusion period, to align it with the expected duration of inclusions, as reported in the rest of the protocol (60 months= 5 years).	Other reason(s) for Amendment:  Updated protocol in line with the CTR  The list of international coordinating investigators has been updated.  A clarification has been added for the recommended imaging examinations (CT Scan or MRI and Bone Scan) that must be performed for the disease assessment according to PCWG3 recommendations.  A section on the sponsor's responsibilities has been added.  Section 11.1 "Independent data monitoring committee": IDMC meeting schedule has been updated to align with the approved IDMC charter.  "G8 Screening tool" (Appendix 7) was updated: age range inconsistency corrected
Summary of the Amendment	Harmonization of the statistical section  Clarification, updating and correction as specified above	

## LIST OF ABBREVIATIONS

Abbreviation	Definition
11C	Choline-11
4-IADL	Instrumental activities of daily living (4 question version)
ADL	Activities of daily living
ADT	Androgen deprivation therapy
AE	Adverse event
AR	Androgen receptor
ASAT	Aspartate aminotransferase
b.i.d	Twice a day ( bis in die )
BMI	Body mass index
BP	Blood pressure
BPI-SF	Brief Pain Inventory - Short Form
BRC	Biological Resource Centre
CI	Confidence interval
CISR-G	Cumulative Illness Score Rating-Geriatrics
cPFS	Clinical progression-free survival
CRA	Clinical research associate
CRPC	Castrate resistant prostate cancer
CT	Computed tomography
CTC	Circulating tumour cells
CV	Curriculum vitae
DDI	Drug-Drug interaction
DILI	Drug-Induced Liver Injury
ECOG	Eastern cooperative oncology group
eCRF	Electronic case report form
EDTA	Ethylenediaminetetraacetic acid
EORTC	European organisation for research and treatment of cancer
EndT	End of Treatment
FCH	Fluorine-18 choline
FDG	Fluorine-18 fluorodeoxyglucose
FFPE	Formalin-fixed, paraffin-embedded
FIM	First in man
G-CODE	Geriatric Core Dataset
GCP	Good clinical practice
HR	Hazard ratio
HRD	homologous recombination deficiency
HSPC	Hormone-sensitive prostate cancer
ICF	Informed consent form
ICH	International conference on harmonisation

Abbreviation	Definition
IDMC	Independent data monitoring committee
INCa	Institut National Du Cancer – French National Cancer Institute
IRC	Independent review committee
IP	Investigational product
ITT	Intent-to-treat
IWRS	Interactive Web Response System
LTFU	Long-term follow-up
LFT	Liver Function Test
M1	de novo metastatic
mg	milligram(s)
mIBG	Metaiodobenzylguanidine
min	minute(s)
mL	millilitre(s)
MRI	magnetic resonance imaging
MSI	microsatellite instability
NCI-CTCAE	National cancer institute - Common terminology criteria for adverse events
nmol	nanomole
OS	Overall survival
PCWG 3	Prostate Cancer Working Group 3
PET	Positron emission tomography
PFS	Progression-free survival
PFS2	PFS after next line of treatment
PIS	Patient information sheet
PK	Pharmacokinetics
po	Oral administration ( Per os )
PSA	Prostate specific antigen
QLQ	Quality of life questionnaire
QoL	Quality of life
RECIST	Response evaluation criteria in solid tumours
rPFS	Radiographic progression-free survival
SACT	Systemic anti-cancer therapy
SAE	Serious adverse event
SAP	Statistical Analysis Plan
SNV	Single nucleotide variation
SOC	Standard of care
SST	Serum-separating tube
TEAE	Treatment emergent adverse event
TMF	Trial Master File

Abbreviation	Definition
TUG	Timed up and go test
WGA	Whole genome amplification

## STATEMENT OF COMPLIANCE

UNICANCER, the trial sponsor, certifies that the trial PEACE 6 Vulnerable will be conducted in compliance with the protocol described in this document, and in accordance with the current Declaration of Helsinki (Appendix 1), the current International conference on harmonisation (ICH) Harmonized Tripartite Guideline for Good Clinical Practice (ICH-GCP, see Appendix 2), the Good Manufacturing Practices (in particular, Annex 13 on investigational medicinal products), Regulation (EU) no 536/2014 of the European Parliament and of the Council on clinical trials on medicinal products for human use,, Regulation (EU) 2016/679 (General Data Protection Regulation) and any national legal requirements.

## PROTOCOL SUMMARY

A) TRIAL IDENTIFICATION	
SPONSOR – PROTOCOL CODE NUMBER: Unicancer - UC-GTG-2006	
VERSION (NUMBER & DATE): Version n° 6.0 – 17Dec2024 -EU	
TRIAL TITLE:  A double-blind randomised phase III trial evaluating the efficacy of ADT +/- darolutamide in de novo metastatic prostate cancer patients with vulnerable functional ability and not elected for docetaxel or androgen receptor targeted agents  PHASE (FOR TRIALS ON MEDICINAL PRODUCTS): Phase 3	
TRIAL TITLE FOR LAY PEOPLE: Randomised phase III trial of ADT +/- darolutamide in frail men with castration-naïve de novo metastatic prostate cancer	
ABBREVIATED TITLE: PEACE 6 Vulnerable	
INTERNATIONAL COORDINATING INVESTIGATOR:  [name] - Gustave Roussy Cancer Campus, France	
NUMBER OF SITES: 100	NUMBER OF PATIENTS: 300

B) SPONSOR IDENTIFICATION	
NAME:	Unicancer [name] [name]
CONTACT PERSON:	[name] [name] Project Manager R&D UNICANCER [contact] email: [contact]

C) TRIAL GENERAL INFORMATION
INDICATION: De novo metastatic Prostate Cancer
TRIAL DESCRIPTION/DESIGN:  This is a Phase III, international, multicentre, randomised, double-blinded placebo controlled trial, evaluating the efficacy and safety of ADT +/- darolutamide in castration-naïve de novo metastatic prostate cancer patients with vulnerable functional ability who have not elected for docetaxel or other androgen receptor pathway inhibitors.  The study plans to enrol 300 patients who will be randomised (1:1) to receive either: 

• Experimental arm: ADT + darolutamide 600 mg po b.i.d

• Control arm: ADT + placebo po b.i.d

Patient participation is divided into 4 phases: Screening, Treatment, End of Treatment (EoT), and Long-Term Follow-up (LTFU).

Following signature of the informed consent form, prospective patients will enter the Screening period (max. 28 days prior to start of treatment) during which all examinations required to assess their eligibility will be performed, including demographic data collection, tumour evaluation and clinical and laboratory evaluations. Eligible patients will be randomised via an interactive web response system (IWRS). For patients who provide their additional consent, the availability of a suitable formalin-fixed, paraffin-embedded (FFPE) biopsy sample of a metastatic site or primitive tumour tissue will be verified during the screening period. France only: Blood samples will also be collected prior to the start of treatment.

Randomised patients will receive ADT plus the investigational product (IP, darolutamide 600 mg), or placebo equivalent as a tablet to be taken orally (po) twice a day (b.i.d). Patients will be asked to attend clinical visits to perform safety and efficacy assessments on Day 30 ( $\pm 3$  days), Day 60 ( $\pm 3$  days), Day 120 ( $\pm 7$  days), Day 180 ( $\pm 7$  days), Day 240 ( $\pm 7$  days) and then every 120 ( $\pm 14$ ) days for the first two years of treatment and every 180 ( $\pm 14$ ) days thereafter. Response to treatment will be assessed according to the Prostate Cancer Clinical Trials Working Group 3 (PCWG3) criteria by radiographic exams performed every 120 ( $\pm 14$ ) days after randomisation during the first 2 years and every 180 ( $\pm 14$ ) days thereafter.

Treatment will be continued until radiographic disease progression according to PCWG3 criteria. Treatment may also be terminated at the initiative of either the patient or the investigator for any reason that would be beneficial to the patient, including: unacceptable toxicity, intercurrent conditions that preclude continuation of treatment, or patient request.

An EoT visit will be performed within 30 ( $\pm 3$ ) days of study treatment discontinuation for any reason. After the EoT visit, patients will enter the LTFU period and will be followed for up to 10 years from the date of randomisation. During this time, information will be collected every 180 ( $\pm 14$ ) days regarding survival status, subsequent antineoplastic treatments, and the status of ongoing AEs and/or new IP related AEs. Patients who discontinue treatment for reasons other than disease progression (e.g. due to toxicity, patient or investigator decision) will continue to be assessed by clinical/laboratory exam and radiographic imaging according to the protocol schedule, until disease progression or initiation of a new antineoplastic treatment, or death.

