## 6. EVALUATION OF TREATMENT EFFICACY AND SAFETY

### 6.1. Efficacy evaluation

Treatment efficacy will be evaluated by measuring changes in tumour size/number of lesions (see Section 7.3.8) and serum PSA levels in response to treatment; according to PCWG3 criteria ([Scher, 2016](#); Appendix 3).

Patient's disease will be assessed at "baseline" (during the screening period) and then every 120 (±14) days after randomisation during the first 2 years and every 180 (±14) days thereafter, until documented radiographic progression, or death, whichever occurs first. For patients who discontinue study treatment for reasons other than radiographic progression, death, or consent withdrawal, investigators will continue to perform disease evaluations during the follow-up period until progression.

The primary evaluation endpoint is radiographic progression-free survival, defined as time from randomisation to radiographic progression according to PCWG3 criteria or death, whichever occurs first.

For secondary evaluation endpoints see Section 3.2.2.

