An EoT visit will be performed within 30 ( $\pm 3$ ) days of study treatment discontinuation for any reason. After the EoT visit, patients will enter the LTFU period and will be followed up for a maximum of 10 years from the date of randomisation. During this time, information will be collected every 180 ( $\pm 14$ ) days regarding survival status, subsequent antineoplastic treatments and the status of ongoing AEs and/or new IP related AEs. Patients who discontinue treatment for reasons other than disease progression (e.g. due to toxicity, patient or investigator decision) will continue to be assessed by clinical/laboratory exam and radiographic imaging according to the protocol schedule, until radiographic progression, or death.

A table summarizing the examination/visit schedule is provided in the "[Schedule of visits and activities](#)" section of the protocol summary.

ADT: Androgen deprivation therapy, bid: Twice a day, CT: Computed tomography, D: Day, EOT: End of treatment, FFPE: Formalin-fixed, paraffin-embedded, MRI: Magnetic resonance imaging, po: Per os (orally), QoL: Quality of life, R: Randomisation, Q: Every, V: Visit, Yrs: Years

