#### 7.4.1. End-of-Treatment Disease Evaluation(s)

Disease evaluation is to be performed as outlined in Section 7.3.8 within 30 ( $\pm$  3) days of last dose of study treatment, or before initiating a new antineoplastic therapy, whichever comes first.

**Note:** If the last radiographic assessment was performed less than 28 days prior to the last dose of study treatment, it does not need to be repeated.

For the patients who discontinued treatment for reasons other than disease progression or withdrawal of consent, tumour assessments should be continued and documented according to the protocol schedule until disease progression (Section 7.5.1).

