#### **7.5.1. Efficacy follow-up**

During the LTFU period, patients who discontinue treatment for reasons other than radiographic disease progression, or withdrawal of consent from the entire study should continue to be assessed by radiographic imaging, PSA and testosterone, ECOG performance status, complete Brief Pain Inventory - Short Form [BPI-SF] and use Opioid therapy according to the protocol schedule, until disease progression or death.

The disease evaluation will be performed according to the methods outlined in Section 7.3.8.

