**Table 5. Censoring rule for primary analysis of radiographic progression-free survival**

Censoring situation	Date of censoring
No baseline assessment	Date of randomisation
No post-baseline assessment and no death prior to first scheduled assessment	Date of randomisation
No radiographic progression or death on study	Date of last tumour assessment
Withdrawn from the study without documented radiographic progression	Date of last tumour assessment

The primary analysis for the rPFS endpoint will be done considering the first radiographic progression observed under study (even if this first radiographic progression is observed under a subsequent line of therapy). As a sensitivity analysis, in case of initiation of a subsequent line of therapy before observing a radiographic progression, the data will be censored at the time of initiation of the salvage treatment.

The final analysis of the primary endpoint will be event-driven, to be performed when at least 197 patients have experienced radiographic progression or death.

Inference for the primary endpoint will be assessed using a two-sided stratified log-rank statistic as the primary analysis. The analysis on stratification factor at randomisation: LATITUDE risk criteria (high risk versus low risk) and ECOG performance status score (0 or 1 vs 2).

A patient is considered as high risk according to the LATITUDE criteria if he has at least two of the three following high-risk factors associated with poor prognosis: a Gleason score of 8 or more (on a scale of 2 to 10, with higher scores indicating more aggressive disease), at least three bone lesions, and the presence of measurable visceral metastasis. He is otherwise considered as low risk ([Fizazi, 2017](#)).

In case the stratification factor does not have sufficient number of patients (less than 3%) and the inferential analyses would be negatively impacted, the stratification factor will not be included as a stratification factor in this analysis.

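### The protocol summary ends scheduled imaging when a new antineoplastic treatment starts, which contradicts the body of the protocol and the primary analysis rule for rPFS

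*Protocol*

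**What the plan says.** **Summary.** Under trial general information, the protocol summary says that patients who discontinue for reasons other than progression continue clinical/laboratory examination and imaging "according to the protocol schedule, until disease progression or initiation of a new antineoplastic treatment, or death".

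**Body and schedule.** Five other places set the same follow-up rule, and none stops at new therapy:

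- Section 6.1: "investigators will continue to perform disease evaluations during the follow-up period until progression".
- Section 7, in a sentence that otherwise nearly repeats the summary: "according to the protocol schedule, until radiographic progression, or death".
- Section 7.4.1: "tumour assessments should be continued and documented according to the protocol schedule until disease progression".
- Section 7.5.1: "according to the protocol schedule, until disease progression or death".
- Footnote (b) to the schedule of visits and activities, attached to CT/MRI, bone scan and PCWG3 assessment in long-term follow-up: these run on schedule until disease progression.

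**Analysis.** In section 10.3.2, the text under Table 5 counts the first radiographic progression "even if this first radiographic progression is observed under a subsequent line of therapy". Only in a sensitivity analysis is a patient who starts another line first handled differently: "the data will be censored at the time of initiation of the salvage treatment". Table 5 censors a patient without progression or death at the last tumour assessment.

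**The concern.** The primary analysis deliberately disregards the start of a later therapy. That works only if scans continue after the switch. The summary sentence, read alone, tells a site to stop them.

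The affected patients are foreseeable. Section 7.4 allows study treatment to be stopped and another therapy started at clinical progression without radiographic progression. Section 5.6 leaves later therapy to the physician. Time to first subsequent systemic therapy is itself a secondary endpoint.

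At a site that stops scanning, such a patient has no observable progression date. For these patients the primary analysis comes close to the planned sensitivity analysis, and the contrast between the two is lost. Clinical worsening may precede radiographic progression, so censoring at the switch can be informative. If switching is more frequent in one arm, the hazard ratio is also distorted, and waiting for more events would not repair that. Sites acting on different parts of the protocol would be measuring different versions of the primary endpoint.

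**Working it through.** **1. The texts side by side**

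| Place | Imaging after early treatment stop ends at | Stops at new therapy? |
|---|---|---|
| Summary, trial description | progression, new antineoplastic treatment, or death | yes |
| Schedule, footnote (b) | disease progression | no |
| Section 6.1 | progression | no |
| Section 7 | radiographic progression or death | no |
| Section 7.4.1 | disease progression | no |
| Section 7.5.1 | disease progression or death | no |
| Section 10.3.2, primary analysis | counts progression under a later line | needs the scans |

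One sentence stands against five others and the analysis rule.

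**2. The plan's own figures reproduce**

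Inputs from sections 10.1 and 10.4: HR 0.65, medians 12 and 18.5 months, two-sided alpha 0.05, power 85%, 150 patients per arm, accrual 18/50/53/179 over 12/12/12/24 months, drop-out hazard 0.014 (taken as per month), interim at 138 of 197 events.

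- Events, fixed design (Schoenfeld): D = 4(1.960 + 1.036)² / (ln 0.65)² = 4 × 8.98 / 0.1856 ≈ 194.
- With the stated boundaries (Z 2.437 and 2.000), power at 197 events is 85.1%.
- Expected events by month T, summed over arms and accrual periods: (n/2) × λ/(λ+δ+σ) × the mean of [1 − exp(−(λ+δ+σ)(T − u))] over entry times u. Here λ = ln 2/12 = 0.0578 (control) or 0.65 times that (experimental), δ = 0.014, and σ is a switching hazard. With σ = 0 and T = 75 this gives 196.7 events, against the stated 197.

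The planning figures are sound and are not part of the problem.

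**3. Possible size, as an assumed range**

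The protocol gives no share of patients who switch before radiographic progression. The figures below are upper bounds: every switcher is at a site that follows the summary, and no death after a switch counts.

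*Equal switching hazard in both arms, unrelated to progression, HR held at 0.65.* The percentage is the share of control patients switching before an event, ignoring drop-out.

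| Switching | Events at month 75 | Power | Most events ever reachable with 300 patients |
|---|---|---|---|
| 5% | 190 | 84% | 219 |
| 10% | 183 | 82% | 208 |
| 20% | 168 | 79% | 186 |
| 30% | 151 | 75% | 164 |

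*Switching shortly before progression.* Simulation with 1,500 trials per row and a cut at month 75.2. Switchers lose their event and are censored at a uniform point in the second half of their progression-free time. A trial rejects at |Z| > 2.0.

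| Control / experimental | Events | HR | Power |
|---|---|---|---|
| none | 197 | 0.65 | 85% |
| 5% / 2.5% | 189 | 0.66 | about 80% |
| 10% / 5% | 182 | 0.67 | about 74% |
| 20% / 10% | 166 | 0.71 | about 58% |
| 20% / 20% | 158 | 0.64 | about 77% |

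**4. Relaxing the worst case**

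- If 30% of switchers' events are deaths that still count: 10%/5% gives 186 events, HR 0.66, power about 80%; 20%/10% gives about 176 events, HR 0.69, power 69%.
- If only 25% of switchers are affected: 20%/10% gives 190 events, HR 0.66, power 78% at month 75.2, or 82% if the trial runs on to 197 events (about month 79).

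The 30%, the 25%, the switching rates and the 2:1 imbalance between arms are all assumptions.

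**The case against.** **The endpoint can be measured.** A reader might infer that rPFS cannot be measured as defined. The protocol does not support that, because sections 6.1, 7, 7.4.1 and 7.5.1 and footnote (b) already require the scans. This objection stands: the defect is one contradictory sentence.

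**Sites need not work from the summary narrative.** Nothing says they do. Section 3.3 names the schedule of activities as defining the examinations, and its footnote (b) carries the consistent rule. This stands too. It lowers the likely number of affected patients but does not remove the contradiction, since the schedule and the conflicting sentence both sit in the summary.

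**Switching may be uncommon.** Section 7.4 says that a rising PSA should not be the lone reason to stop, so only the route through clinical progression is clearly supported. Patients are also ineligible at entry for docetaxel, abiraterone, enzalutamide and apalutamide. Section 7.4.1 asks for a disease evaluation before a new therapy starts, unless a recent one exists, so progression already visible at the switch is captured. These points limit the size. They do not help with progression that appears after the switch, which is what section 10.3.2 means to count.

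**Section 7.3.8 is not a second conflict.** Its wording that evaluations run until treatment discontinuation might look like one, but it belongs to the treatment-period visits. Sections 7.4.1 and 7.5.1 govern what follows.

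**Conclusion.** The contradiction is certain from the text. The summary's stop at new antineoplastic treatment conflicts with footnote (b), with sections 6.1, 7, 7.4.1 and 7.5.1, and with the primary analysis in section 10.3.2. At any site that follows it, patients who switch before radiographic progression are censored at the last scan or counted only at death.

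The consequence is uneven collection of primary-endpoint data, with possible loss of events and informative censoring. Its size cannot be derived from the protocol. As an upper bound under assumed switching of 10% control and 5% experimental with all switchers' events lost, there are about 182 events and HR 0.67 at month 75, against 197 and 0.65. The real effect is smaller if deaths count or only some sites follow the sentence.

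A reader might take the 58% power in the 20%/10% row as the expected loss. It is not: it combines unsourced rates, an assumed arm imbalance, full adherence to the outlying sentence and a fixed cut-off in an event-driven analysis. With equal switching, the simulated HR stays at about 0.64, so the loss there is of events and time only.

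**What to change.** In the protocol summary, delete the words on initiation of a new antineoplastic treatment from the follow-up sentence, so that it matches sections 7 and 7.5.1 and the analysis in section 10.3.2. Notify sites that scheduled imaging after early treatment stop continues to radiographic progression or death, whether or not new therapy starts.

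The cost is one clause in the next amendment and a site letter. No procedure is added, because the body already requires these scans. Section 7.3.8 needs no change. The 300 patients, 197 events and 85% power stand. The letter should go out promptly: about 115 of 300 patients were enrolled at this amendment, and scans not taken cannot be recovered later.

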#### PRIMARY OBJECTIVE:

To compare the efficacy of ADT + darolutamide vs ADT + placebo in terms of radiographic progression-free survival (rPFS) in patients with castration-naïve *de novo* metastatic prostate cancer with vulnerable functional ability and not elected for docetaxel or other androgen receptor pathway inhibitors.

